4. SELECTION AND ENROLLMENT OF SUBJECTS

4.1 INCLUSION CRITERIA

1. Patient age is between 18 to 70, inclusive
2. Historical modified Rankin Scale Score 0-1
3. Aneurysmal subarachnoid hemorrhage caused by a ruptured saccular aneurysm confirmed by catheter angiography that is repaired by endovascular coil embolization. Initiation of the coil embolization procedure should occur within 48 hours from the time of the aneurysm rupture (ictus). In patients where the exact time of the ictus is uncertain, a reasonable estimate of the time of ictus may be assigned. This reasonable time estimate should be considered likely accurate to within hours of the true unknown time.

4. Quality of aneurysm embolization is interpreted to be Raymond-Roy Score of 1 (Complete) or 2 (Residual Neck) indicating that the aneurysm is adequately secured. A tiny amount of contrast in the body of the aneurysm is acceptable as long as the physician considers the aneurysm secured and to NOT represent a Raymond-Roy Score of 3 (Residual Aneurysm). Please see diagram below:

5. WFNS grade 1 or 2 as assessed after repair of the aneurysm during screening but prior to randomization. A patient who presents with a WFNS greater than 2 who then improves with resuscitation, ventriculostomy, or time is acceptable.

- The modified GCS (mGCS) is the sum of the best eye-opening response, the best verbal response and the best motor response (best extremity). It is used to determine the WFNS according to the tables below:

Adult modified Glasgow Coma Scale (mGCS)

Test	Responses	Value
Eyes opening Response (1-4)	No Response	1
	to pain	2
	to voice	3
	opens eyes spontaneously	4
Verbal Response (1-5)	No Response	1
	Incomprehensive words	2
	Inappropriate words	3
	Disoriented	4
	Oriented	5
Motor Response (1-6)	No Response	1
	Abnormal extension (decerebrate posturing)	2
	Abnormal flexion (decorticate posturing)	3
	Withdrawal	4
	Localizes	5
	Follows Commands	6

World Federation of Neurological Surgery (WFNS) SAH Grading Scale

[figure not shown]
WFNS Grade	mGCS Score	Motor Deficit
1	15	Absent
2	14 - 13	Absent
3	14 - 13	Present
4	12 - 7	Present or Absent
5	6 - 3	Present or Absent

- For patients with endotracheal intubation, we calculate (impute) a mGCS verbal score based on a table comparing the mGCS eye opening response and best motor response scores. In the table below, the green shaded areas represent patients that would continue to meet enrollment criteria based on mGCS score contribution to the WFNS grade (total mGCS of 13-15). This alleviates the challenge of not being able to directly assess the mGCS verbal score due to the patient being intubated during the assessment.

mGCS Verbal Score for Patients that have Endotracheal Intubation

Motor Score (1-6)	Eye Score (1-4)			
	1	2	3	4
1	1	1	1	2
2	1	2	2	2
3	2	2	3	3
4	2	3	3	4
5	3	3	4	4
6	3	4	4	5

- The pre-repair, admission head CT demonstrates an aSAH bleed pattern of “thick and diffuse” or “thick and focal” hemorrhage within the subarachnoid basal cisterns measuring ≥ 4 mm in the short axis and ≥ 20 mm in the long axis which is consistent with a modified Fisher grade 3 or 4. Intraventricular hemorrhage is acceptable. Enrollable patients must **NOT** have a parenchymal hemorrhage greater than 10 cc. Please refer to diagram below for examples. The hemorrhage location should be substantially within the supratentorial space and not isolated to the infratentorial space.

The Modified Fisher CT rating scale: Grade 1 (minimal or diffuse thin SAH without IVH); Grade 2 (minimal or thin SAH with IVH), Grade 3 (thick cisternal clot without IVH), Grade 4 (thick cisternal clot with IVH) [From: Claassen J et al. Effect of cisternal and ventricular blood on risk of delayed cerebral ischemia after subarachnoid hemorrhage: the Fisher scale revisited. *Stroke* 2001;32:2012-2020.]

7. The location of the aneurysm should be the anterior circulation, posterior communicating, **OR** a basilar terminus (apex). Angiographic location of the aneurysm should be confirmed by catheter digital subtraction angiography (DSA) usually obtained during the coil embolization procedure. Patients with PICA or other posterior circulation aneurysms as the cause of the SAH should not be included because they typically cause primarily infratentorial bleed patterns.
8. Ability to screen the patient and obtain a head CT 2-12 hours after the completion of the coiling procedure and the ability to initiate the study drug 12 ± 4 hours after the completion of aneurysm coiling procedure.
9. After recovering from anesthesia following the aneurysm coiling procedure, the patient must remain a WFNS SAH grade ≤ 2 without evidence of a significant new focal neurological deficit including monoparesis / monoplegia, hemiparesis / hemiplegia, or receptive, expressive or global aphasia. New minor cranial nerve defect without any other new findings is permissible. If an NIHSS score was obtained prior to the aneurysm coiling procedure, a post-coiling (pre-enrollment) NIHSS score must not have increased by ≥ 4 points and GCS score must not be decreased by ≤ 2 points. The clinician at the local site should use their best clinical judgment as to whether a significant neurological decline has occurred due to the procedure.

10. Patient is willing and able to return for study follow-up visits.
11. Patient or their Legally Authorized Representative (LAR) has provided written informed consent.

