STUDY POPULATION	
Patients with a supratentorial aSAH secondary to a ruptured cerebral aneurysm that has been secured by endovascular coil embolization. Study subjects must score as a WFNS SAH grade ≤ 2 post-coiling with no significant aphasia at the time of enrollment and have a significant hemorrhage burden on the initial head computed tomographic (CT) scan that demonstrates a modified-Fisher grade 3, or grade 4 (with minimal intraparenchymal blood or IVH less than 25%.)

CLINICAL SITES	
Eight to ten designated clinical sites in the USA.

PLANNED ENROLLMENT	
88 patients (44 in each treatment allocation group; Approximately 5-6 patients per site per year average)

STUDY DURATION	
3 years [2 years enrollment; 3 months primary end-point follow-up visit; 3 months data analysis and reporting of results; 1-year follow-up visit secondary endpoint].

PRIMARY SAFETY ENDPOINT	
Rate of “Major Bleeding” or “Clinically Relevant Non-Major Bleeding” as defined by the International Society of Thrombosis and Haemostasis (ISTH) between the groups from enrollment until discharge from the acute inpatient setting.

SECONDARY SAFETY ENDPOINT	
Rate of Symptomatic Intracranial Hemorrhage between the two groups from enrollment until discharge from the acute inpatient setting. A symptomatic hemorrhage is defined as a 4-point or greater increase in the NIHSS or a decrease in the GCS by 2 or more points not explained by other causes.

ADDITIONAL PRESPECIFIED SAFETY OUTCOMES TO BE ANALYZED	
Rate of any new intracranial hemorrhage between the two groups from enrollment until discharge from the acute inpatient setting.
 
Rate of Serious Adverse Events (SAEs) between the two groups from enrollment until

the 90-day follow-up visit as reported by each site and adjudicated by an independent Clinical Events Adjudication Committee (CEC).

Rate of Type II Heparin Induced Thrombocytopenia (HIT) between the two groups from enrollment until the 90-day follow-up visit

Rate of DVT or PE between the two groups from enrollment until the 90-day follow-up visit

All cause and neurological mortality rates between the two groups from enrollment until the 90-day follow-up visit

PRIMARY CLINICAL EFFECT ENDPOINT

Mean Montreal Cognitive Assessment score (MoCA) at 90 (± 10) days post enrollment.

SECONDARY ENDPOINTS:

-PRIMARY BIOMARKER ENDPOINT

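### The GCS clause in inclusion criterion 9 points the opposite way from the NIHSS clause beside it, so read literally it bars every fall still compatible with WFNS ≤ 2, including 1-point falls

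*Protocol*

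**What the plan says.** Criterion 9 in Protocol section 4.1 applies after recovery from anesthesia. It first requires that "the patient must remain a WFNS SAH grade ≤ 2 without evidence of a significant new focal neurological deficit". It then adds a numerical comparison with the pre-coiling state, which applies only if an NIHSS was obtained before the procedure: "NIHSS score must not have increased by ≥ 4 points" and "GCS score must not be decreased by ≤ 2 points". The criterion closes by saying that the site clinician "should use their best clinical judgment as to whether a significant neurological decline has occurred due to the procedure".

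Two other places bear on the point:

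- Criterion 5 in the same section requires "WFNS grade 1 or 2 as assessed after repair of the aneurysm during screening but prior to randomization". The table for intubated patients below it gives the matching score range as "total mGCS of 13-15".
- The secondary safety endpoint in section 1.1 counts a hemorrhage as symptomatic on a "4-point or greater increase in the NIHSS or a decrease in the GCS by 2 or more points", provided other causes do not explain the change.

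**The concern.** Both halves of the criterion 9 sentence are meant to detect a patient who got worse between the pre-coiling and post-coiling examinations. The NIHSS half does so by barring large rises. The GCS half, taken at its word, bars small falls and is silent on large ones.

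This is an operative threshold. Section 6.4 says that patients should not be randomized until all eligibility criteria are met, section 6.1 has reasons for non-enrollment logged and reviewed for systematic bias, and section 10.4 has on-study protocol violations presented. A site that follows the text turns away a patient who went from 15 to 14. A site that reads the clause in the same direction as the NIHSS half may enroll that patient and be formally in deviation. Eligibility, screening-log reasons and deviation counts could then differ between sites because of the wording. Randomization is not stratified by site, and site is to be handled in the analysis.

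**Working it through.** The plan gives no figure to reproduce. The check is an enumeration of possible score changes.

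**Inputs**
- GCS range 3 to 15, from the scale printed under criterion 5.
- WFNS grade by score, from the table under criterion 5: grade 1 is 15; grade 2 is 13 or 14 without motor deficit; grade 4 is 7 to 12; grade 5 is 3 to 6.
- The clause as written: a fall of 2 or less is barred.
- The direction used in the endpoint: "a decrease in the GCS by 2 or more points not explained by other causes".

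**Assumptions**
- The GCS in criterion 9 and the modified GCS behind the WFNS grade are the same 3-to-15 score.
- An unchanged score is not a decrease.

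**Step 1, the clause alone.** Fall = score before − score after. The largest possible fall is 15 − 3 = 12. As written, falls of 1 and 2 are barred, and falls of 3 to 12 are not.

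**Step 2, add WFNS ≤ 2.** The score after coiling must be at least 13, so the largest fall that can keep a patient eligible is 15 − 13 = 2. A fall of 3 from the top of the scale gives 15 − 3 = 12, which is grade 4.

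**Step 3, list the cases.**

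| Before → after | Fall | WFNS after, no motor deficit | Clause as written | Direction of the endpoint |
|---|---|---|---|---|
| 15→14 | 1 | 2 | barred | not barred |
| 14→13 | 1 | 2 | barred | not barred |
| 15→13 | 2 | 2 | barred | barred |
| any | 3 to 12 | 4 or 5 | not barred | barred |

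The last row is excluded by the WFNS requirement whichever way the clause runs.

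**Step 4, is the literal reading plausible?** Among patients who still meet WFNS ≤ 2, the literal clause bars all three possible falls. It therefore acts as a ban on any decrease, and the figure 2 does no work. A rule meant to ban any decrease would need no number. The last column is shown only to compare directions; it does not establish what threshold criterion 9 should use.

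**The case against.** The best case for leaving the text alone has several parts.

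- **Large falls are already caught.** A reader might infer from the reversed sign that badly deteriorated patients could be enrolled. The documents do not support that. Criteria 5 and 9 both require WFNS ≤ 2, no fall of 3 or more can meet it, and criterion 9 also bars significant new focal deficits and aphasia. This part stands in full.
- **Criteria apply jointly.** It is tempting to say that a patient at WFNS grade 2 is declared eligible by criterion 5 and then wrongly removed by criterion 9. Criterion 5 is necessary, not sufficient, so a later criterion may properly remove a patient whom it accepts. The contradiction lies in the direction of the inequality, not between criteria 5 and 9. This stands.
- **The endpoint is not a general definition of worsening.** It defines symptomatic hemorrhage and carries a qualifier about other causes. It shows which way the protocol runs this pair of scales, but it does not settle the eligibility threshold. This stands.
- **The sentence is conditional and followed by clinical judgment.** The condition on a pre-coiling NIHSS narrows the reach, although the Schedule of Events (section 15.1) marks NIHSS and GCS in the 0-to-48-hour column, so it should often be met. The judgment sentence points toward a sensible reading, but it does not say that it overrides the numerical bar and may itself be applied differently by site. This stands in part.
- **One symbol in machine-read text.** The sign should be checked against the source file. The same sentence prints the opposite sign correctly for NIHSS, which makes a reading error less likely but does not rule it out.

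**Conclusion.** The point holds as a directional inconsistency in an eligibility criterion. The GCS clause conflicts with the NIHSS clause in its own sentence and with the same pair of scales in the symptomatic hemorrhage endpoint. Where a pre-coiling NIHSS exists, the literal text bars all three falls compatible with WFNS ≤ 2, and two of those are 1-point falls. In the endpoint's direction, one of the three would be barred.

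The consequence is unintended exclusion and inconsistent application across 8 to 10 sites, in a trial planning 88 patients at about 5 to 6 per site per year. A reader might infer a material loss of accrual. The documents do not support a figure: they give neither the frequency of 1- or 2-point falls after coiling nor how sites read the clause. The conclusion rests on the two assumptions stated in the working and on the sign being printed as read. It is a wording correction worth making, not a threat to the safety of enrollment.

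**What to change.** First confirm the sign in the source file. Then amend criterion 9 so that the direction of its GCS inequality is reconciled with the NIHSS half of the sentence and with the symptomatic hemorrhage endpoint in section 1.1. The sponsor should confirm which GCS threshold is intended; the documents do not settle it, and it should not be taken over from the hemorrhage endpoint by default. The amendment should also say whether the clinical-judgment sentence can override the numerical rule.

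Carry the same wording into the eligibility check on the case report form. If enrollment has begun, review the screening logs for patients excluded on this clause and the deviation records for patients enrolled against it.

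The cost is a one-symbol protocol amendment if the number stays as it is, a short clarifying statement on judgment, a form edit and a short note to sites. No change to sample size or analysis follows.

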4.2 EXCLUSION CRITERIA

1. Angio-negative SAH.
2. History or imaging suggesting that the current hemorrhage presentation is a recent re-rupture of the aneurysm. Prior sentinel headache with negative CT or prior sentinel headache where the patient did not seek medical attention does not exclude the patient.
3. Surgical Clipping (or plan for clipping) of the ruptured aneurysm or any non-ruptured aneurysm on the same admission.
4. Aneurysm is identified to be traumatic, mycotic, blister or fusiform type by catheter DSA.
5. Any intracranial stent placement or non-coil intra-aneurysmal device where dual-antiplatelet therapy is needed during admission.
6. Patient has additional aneurysm(s) that are untreated and could reasonably be considered a possible alternate cause of the aSAH based on the observed bleeding pattern. Adequate treatment of these aneurysms by coiling embolization would result in the aneurysms no longer causing an exclusion. MRI may be used in some situations to determine that the associated aneurysms did not rupture based on lack of blood seen adjacent to the additional aneurysms.
7. Patient received heparin in any form within the last 100 days prior to current presentation / admission.
8. Thrombocytopenia (platelet count less than 100,000 - assuming clumping has been ruled out as a cause).
9. New intraparenchymal hemorrhage or new infarction larger the 15cc in volume, or significant increased mass effect as seen on the post-coiling, pre-enrollment head CT when compared to baseline admission head CT. New hyperdensity on CT scan related to contrast staining is not an exclusion.

10. Patient has a documented history of heparin induced thrombocytopenia (HIT).
11. Patient developed SAH-induced cardiac stunning prior to enrollment, with an ejection fraction <30%, or requiring IV medications for blood pressure maintenance.
12. Thrombolytic therapy within 24 hours prior to enrollment (rtPA, urokinase, etc.)
13. Plan for antiplatelet or oral anticoagulation therapy from the time of the coil embolization procedure until 14 full days after enrollment. Antiplatelet therapy may be resumed after the 14-day window. A single 325 mg Aspirin (or lower dose) given during the coil embolization peri-procedural period is acceptable if this is the local standard of care but should be documented.
14. Concomitant serious or uncontrolled disease such as severe infection, active (non-remission) cancer, severe organ dysfunction (severe heart failure, severe chronic kidney impairment requiring dialysis or severe chronic liver disease) or any coagulopathy (including DIC or bleeding diathesis).
15. Uncontrollable hypertension (>180 systolic and/or >110 diastolic) that is not correctable prior to enrollment.
16. Prior neurological disease/deficit or psychiatric disease that may continue to alter the results of neuropsychological evaluation, such as dementia, Multiple sclerosis, seizure disorder, severe traumatic brain injury, previous ruptured cerebral aneurysm or active major depression. Childhood seizures that have resolved and no longer require treatment are not part of this exclusion criteria.
17. Active Immunosuppression therapy including chronic corticosteroid usage.
18. History of gastrointestinal hemorrhage or major systemic hemorrhage within 30 days (including large flank or large retroperitoneal hematoma due to current admission coiling procedure requiring treatment), hemoglobin less than 6 g/dL, INR \geq 1.5 after reversal of anticoagulants.
19. Major surgery (including open femoral, aortic, or carotid surgery) within previous 30 days.
20. Currently pregnant.
21. Enrollment in another research study that prescribes a therapeutic treatment that differs from the local standard of care, or that would conflict with this study in some other significant fashion. Registries or coil comparison studies are appropriate.

4.3 Rationale For Selecting The Target Patient Population

Modified-Fisher grade 3 or 4 aSAH patients with good baseline neurological function (WFNS \leq 2) are the ideal patient population for several reasons:

- Focusing on a patient subgroup with homogenous baseline characteristics will favor uncovering a treatment effect with a small sample size
- This specific subgroup is similar to study patients where a similar LDIVH protocol was previously shown to be effective in a retrospective human study.
- These patients are most likely to experience, neuroinflammation, vasospasm and other causes of DNDs due to the high hemorrhage burden and therefore most likely to have the opportunity to show benefit from UFH administration.
- These patients are least likely to have a confounding significant pre-existing neurological injury due to the initial rupturing of the aneurysm prior to initiation of the LDIVH study drug.

4.4 Study Enrollment Procedures

Due to the acute nature of the disease process being studied, there will not be any media advertising for enrollment within this study. Potential participants will be identified by members of the study team as they are a part of the typical patient population for these healthcare providers and clinical sites. Identification and recruitment of study subjects will be done at participating institutions under the supervision of the local site PI and study team. All patients admitted for acute aSAH under the care of study personnel may be identified as potential candidates for screening, including minorities, young adults aged 18-21 years old, women (excluding those who are pregnant), and other underrepresented research populations. The screening, informed consent, randomization and enrollment procedures are detailed below in Section 6.1-6.5. A patient is considered enrolled in this study after informed consent has been obtained **AND** the patient has met all enrollment criteria **AND** has been randomized to a treatment allocation arm.

5. STUDY INTERVENTIONS

5.1 Study Drug

The study drug will be unfractionated heparin intravenous solution with a concentration of 100 units per ml. UFH will be provided and prepared by the investigational / research pharmacy at each clinical site. UFH is a glycosaminoglycan (GAG). GAGs are a physiologically reactive class of acidic, negatively charged, structurally and functionally similar polysaccharides. They are long-chain compounds composed of repeating disaccharide units having a carboxyl group and one or more sulfates, in which one

sugar is N-acetylgalactosamine or N-acetylglucosamine. The endogenous GAGs are heparin, heparan sulfate, keratin sulfate, dermatan sulfate, chondroitin-4-sulfate, chondroitin-6-sulfate and hyaluronic acid.

Metabolism

For UFH, the liver and the reticuloendothelial systems are the sites of biotransformation. Elimination of UFH is thought to be primarily via the reticuloendothelial system, with uptake by the same Hyaluronic acid receptor for endocytosis (HARE receptor) on the sinusoidal epithelium of reticuloendothelial cells that eliminates heparin from the circulation. Renal excretion possibly plays a minor role.

UFH Safety in Humans

UFH has been used as a medical therapy for anticoagulation purposes for decades and its risk profile is well established. LMWHs and heparinoids often cause a temporary class effect related to transient elevation of liver enzymes. This occurs on approximately day 5 - 7 of exposure, with return to baseline values by day 14 after treatment discontinuation. These elevations should be evaluated cautiously as they could confuse diagnosis of myocardial infarction, liver disease, and other disorders.

Osteoporosis has been reported as a class effect for chronic usage of UFH and LMWH. The pathophysiology behind this remains poorly defined.

Bleeding and Heparin Induced Thrombocytopenia are potentially serious side effects that can be related to heparin usage in patients. [Please see sections on HIT and definitions of serious bleeding that can be found later in this protocol].

5.2 Dose Selections And Treatment Duration

This study will plan to infuse the study drug UFH in an escalating fashion with a minimum target rate of 12 u/kg/hr and until a goal aPTT is achieved. The aPTT should be maintained at that level for up to 14 days of study drug infusion. The study drug infusion will begin 12 hours +/- 4 hours after the aneurysm treatment procedure is completed. **The initial infusion rate will be 8 units/kg/hr.** An aPTT will be checked 6 hours later and if a therapeutic level is not achieved the rate will be increased to 10 u/kg/hr 12 hours after study drug initiation. An aPTT level will again be checked 6 hours after the rate increase and the rate will be increased again by 2 u/kg/hr to 12 u/kg/hr, 12 hours after last adjustment until the aPTT goal is reached and then the study drug infusion will be maintained at that level with periodic aPTT levels being checked to confirm that the target aPTT is maintained. Additional upward dose rate adjustments after reaching 12 u/kg/hr (if needed) should be by 1u/kg/hr to avoid overshooting the aPTT goals which could increase the risk of hemorrhage. **The maximum hourly rate of the LDIVH infusion should be 1800 units / hour regardless of patient weight.**

The reason for the dose escalation is to mirror a previously reported protocol (Maryland LDIVH protocol) where LDIVH has been administered safely to over 100 aSAH patients treated with craniotomy and clipping without any hemorrhagic complications. The

divergence from that procedure (8 to 9 to 10 u/kg/hr) is to currently initiate the infusion at 8 units/kg/hr and then increase to 10 u/kg/hr and then again to 12 u/kg/hr. This modification was put into effect and is currently being used at the University of Maryland due to the recent (October 2009) reevaluation of UFH potency by the FDA and the United States Pharmacopeia (USP) that resulted in an approximate 10% reduction in heparin potency within the United States in October 2009 compared to previous years. [<http://www.fda.gov/Drugs/DrugSafety/PostmarketDrugSafetyInformationforPatientsandProviders/ucm184502.htm>]

The other area of divergence is that the Maryland LDIVH protocol set a specific target infusion rate (10 or 12 units/kg/hr) regardless of the drug's effect on an individual patient. Variability in aPTT test values in these patients highlighted that the rate of metabolism of UFH varies among patients and therefore we expect the clinical effect to likewise vary among patients when a steady rate of infusion is maintained for all patients. **Our current protocol allows for adjustments of the rate of infusion up or down from 12 units/kg/hr to achieve a target aPTT for each patient that is institution specific and correlates with an anti-Xa heparin assay value of 0.1 – 0.3 IU/ml. The highest rate of heparin that consistently allows subjects at an institution to remain within the desired aPTT goal range is preferred such that the upper end of the target range is more desired over the lower end of the target range. Adjusting the rate by less than 1 unit/kg/hr is not allowed.** The anti-Xa values recommended for heparin anticoagulation therapy (for DVT or PE treatment therapy) are between 0.3 to 0.7 IU/ml. Therefore targeting aPTT values that correlate with 0.1 - 0.3 IU/ml anti-Xa values will provide a consistent, low-level, continuous systemic heparin effect while minimizing the risk of hemorrhagic complications. Routine adjusting of the LDIVH drip will be done with aPTT testing and not with Anti-Xa testing.

Maintaining the aPTT in the target range is important to avoid potential hemorrhagic complications while attempting to maximize the potentially beneficial anti-inflammatory effects of the study drug. Hemorrhagic complications could occur secondary to an anticoagulation effect in aSAH patients treated with coil embolization secondary to the femoral arteriotomy access site (i.e., risk of life threatening retroperitoneal hemorrhage) or inadequate embolization of the ruptured cerebral aneurysm, or secondary to ventriculostomy placement. The anticoagulation effect maintained below the anticoagulation therapeutic window should reduce the chance of a hemorrhagic complication in these subjects.

The time of treatment initiation and duration was selected for several reasons. We elected to start the infusion 12 hours following the procedure to minimize any complications related to temporal proximity to the procedure and to allow time for adequate post-procedure neurological assessment following general anesthesia / extubation. This delay in infusion from the procedure time was used in the Maryland LDIVH protocol in post-craniotomy patients. Delaying initiation of the study drug longer may reduce any treatment benefit as the inflammatory process likely begins to establish itself soon after the hemorrhage event and it may be easier to modulate this inflammatory response in earlier phases before the peak intensity of the inflammatory

response is reached. In the majority of aSAH patients who develop cerebral vasospasm and delayed cerebral ischemia, vasospasm begins to significantly improve by the 14th day following the hemorrhage ictus. It is believed that the majority of the delayed neurological deficits that do occur happen within this window of time, therefore a maximum 14 day LDIVH infusion seems to have the maximal opportunity to benefit the study patients. Previous retrospective human studies of UFH using the Maryland LDIVH protocol showed benefit with infusions up to 14 days.

